# **Gene-Environment Interaction on Adiposity, Glycemic, Lipids Changes and Bone Health: Study Protocol with Statistical Analysis**

## **1. Objective**

The purpose of this study is to test the interactions between the genes and diet interventions varying in macronutrient intake on glycemic, waist circumference, body weight, visceral fat, lipids changes and bone health. In the POUNDS LOST, all of the 811 participants DNA was extracted from the buffy coat fraction of centrifuged blood using the QIAmp blood kit (Qiagen, Chatsworth, CA). Single nucleotide polymorphisms were genotyped using the OpenArray™ SNP genotyping system (BioTrove, Woburn, MA). The study is only accepting participants in the Boston, Massachusetts or Baton Rouge, Louisiana area. For further enrollment information in Boston or Baton Rouge, see Eligibility Criteria or Design Narrative.

Besides, the investigators integrated novel pathway analyses in large cohorts and comprehensive genetic analyses on long-term weight loss and mechanisms in randomized diet intervention trials would provide very important evidence to unravel the etiology of obesity, and have significant public health and clinical implications. Establishing relationship between genetic variants and diets in determining weight change will help identify individuals at high risk for obesity especially when adherent to specific diet.

The epidemic of obesity has become a major public health problem. Obesity is a multifactorial abnormality that has a genetic basis but requires environmental influences to manifest. Common-form obesity is underpinned by both environmental

and genetic factors. Recent genome-wide association studies have identified several genes convincingly related to obesity risk. Testing gene-environment interaction is a relatively new field. Evidence from association studies and intervention trials continues to mount, indicating that genetic components may modify lifestyle effects on the development of obesity. However, these findings are at most preliminary. The interplay between genetic and environmental components may facilitate the choice of more effective and specific measures for obesity prevention based on the personalized genetic make-up.

## **2. Design and Methods**

[figure not shown]
The investigators aimed to examine whether the genetic variation affected glycemic, waist circumference, body weight, visceral fat, lipids, and bone mineral density (BMD) changes in response to weight-loss dietary intervention varying in macronutrient intake (target percentages of energy derived from fat, protein, and carbohydrate in the 4 diets were as follows 20%, 15% and 65%; 20%, 25%, and 55%; 40%, 15%, and 45%; and 40%, 25%, and 35%).

The primary outcome is to test the interactions between the genes and diet interventions varying in macronutrient intake on body weight changes. The secondary outcome is to test the interactions between the genes and diet interventions varying in macronutrient intake on glycemic, waist circumference, visceral fat, lipids, and BMD changes. Understanding gene–diet interactions in relation to weight loss holds great promise for delivering more efficient prevention and treatment on obesity and related metabolic disorders.

We assessed overall genetic variation by calculating a genetic risk score (GRS). The GRS was calculated based on the SNPs by summing risk allele' s numbers, and weighted by their effect sizes ( $\beta$  -coefficients) derived from genome-wide association meta-analyses data (Supplementary Table 1). The GRS was computed using the equation:  $GRS = (\beta_1 \times SNP1 + \beta_2 \times SNP2 + \dots + \beta_n \times SNPn) \times (n/\text{sum of the } \beta \text{ -coefficients})$ , where  $\beta$  is the  $\beta$  -coefficient of each SNP for higher levels of fasting glucose, SNP1, SNP2  $\dots$  and SNP n indicate the number of risk alleles (0, 1 or 2) for each SNP.

The Hardy-Weinberg equilibrium and comparison of categorical variables at baseline were assessed with chi-square test. Differences in continuous variables according to tertiles of the GRS(genetic risk score) at baseline were tested using general linear models, with adjustment for age, sex, and race. The investigators used general linear models to test changes in adiposity, glycemic and lipids traits in high-fat and low-fat diets groups according to tertiles of the GRS. Covariates adjustment included age, sex, race, physical activity, smoking, alcohol, seasonal variation, and the baseline value for the respective outcome in model. Moreover, to analyze the potential interactions between GRS and diet interventions, an interaction product term of GRS-diet was included in the models. As a secondary analysis, with the use of time as a repeated variable, linear mixed models were used to test the GRS effect on the trajectory of changes in adiposity, glycemic and lipids traits by including a GRS-by-time interaction term. Because our analysis is hypothesis-driven and primarily focused on the GRS (rather than individual SNPs), we did not adjust for multiple testing. The level of significance for all tests was set to  $P < 0.05$ . Statistical analyses were performed with SAS version 9.2 (SAS Institute, Inc., Cary, NC).

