#### **4. Baseline Characteristics**

**Arm/Group Information:** Participants were randomly distributed to one of four diets that composed a two-by-two factorial design: 1) a low-fat, average-protein diet (20% fat, 15% protein, and 65% carbohydrate, 2) a low-fat, high-protein diet (20% fat, 25% protein, and 55% carbohydrate), 3) a high-fat, average-protein diet (40% fat, 15% protein, and 45% carbohydrate), and 4) a high-fat, high- protein diet (40% fat, 25% protein, and 35% carbohydrate).

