**Measure of Dispersion/Precision:**

Standard Deviation

**Unit of Measure:** Body weight: weight in kilograms

glycemic changes: mg/dL for fasting glucose, uU/mL for fasting insulin

waist circumference changes: cm

visceral fat changes:(%)

lipids changes: mg/dL for Total cholesterol, HDL cholesterol, LDL cholesterol and

Triglycerides

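### The randomised protein factor has no specified analysis, and the GRS-diet interaction term defines neither the diet coding nor the form of the GRS

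*Combined protocol and SAP*

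**What the plan says.** All references are to the combined protocol and SAP.

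- **Design** (section 4, Arm/Group Information): "Participants were randomly distributed to one of four diets that composed a two-by-two factorial design". The factors are fat at 20% or 40% of energy and protein at 15% or 25%.
- **Primary question** (section 2, repeated in section 5): "The primary outcome is to test the interactions between the genes and diet interventions varying in macronutrient intake on body weight changes". Section 5 sets the time frame at Year 2.
- **Score** (section 2): "The GRS was calculated based on the SNPs by summing risk allele" counts, weighted by published effect sizes. It is a quantitative score before any grouping.
- **Main model** (section 2, statistical paragraph): general linear models were used to "test changes in adiposity, glycemic and lipids traits in high-fat and low-fat diets groups according to tertiles of the GRS". The covariates are age, sex, race, physical activity, smoking, alcohol, season and the baseline value of the outcome. Protein is not among them.
- **Interaction** (same paragraph): "an interaction product term of GRS-diet was included in the models". Neither component is defined further.
- **Longitudinal model** (same paragraph): "linear mixed models were used to test the GRS effect on the trajectory of changes in adiposity, glycemic and lipids traits". The term named is GRS by time; no diet term is named.
- **Error rate** (same paragraph): "The level of significance for all tests was set to" P < 0.05, without adjustment for multiplicity. Sidedness is not stated.

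**The concern.** The primary question concerns diets that differ in fat, protein and carbohydrate, and participants were randomised on two factors. The analysis text mentions one of them. Followed as written, the plan leaves the gene-by-protein question, which the design can answer, without a specified test.

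The primary test is also open in both its parts. Diet could be the fat factor, the protein factor or four arms; the GRS could be continuous or in tertiles. That gives 3 × 2 = 6 candidate tests on body weight alone, and more if tertiles can enter either as a trend or as a factor. Since the plan makes no multiplicity adjustment, nothing in it prevents the choice from being made after results are seen. If the choice falls on tertiles, power is lost for no gain in the test.

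**Working it through.** The documents give no power, effect size, SD or dropout figure, so there is no planned figure to reproduce. Two things can be checked: what tertiles would cost, and what adding protein would cost.

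**Inputs.** N = 811 (sections 4 and 5); alpha 0.05 (section 2). Assumed: two-sided tests, a roughly normal GRS, a linear GRS effect, equal allocation to the four diets (about 811/4 = 203 per diet), and a residual SD of 1, so that effects are in outcome SDs.

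**1. Information kept by tertiles.** Score the tertiles −1, 0, 1. With a standard normal GRS the cut is at z = 0.4307, where the normal density is φ = 0.3636.

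Squared correlation with the continuous score = [2φ(0.4307)]² / (2/3) = 0.7272² / 0.6667 = 0.793.

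The loss is 1 − 0.793 = 20.7%. In participants, 811 × 0.793 = 643, so the equivalent of 168 is lost. Simulated weighted allele scores built from 5 to 97 SNPs kept 76% to 82%, so the result does not depend on exact normality.

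**2. Effect on power.** Take an interaction that has 80% power with the continuous score. Its noncentrality is (1.960 + 0.842)² = 7.85.

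- Tertile trend, 1 df: √(7.85 × 0.793) = 2.495; power = Φ(2.495 − 1.960) = 70%.
- Tertile factor, 2 df: noncentrality 7.85 × 0.793 = 6.23 against a critical value of 5.99; power = 60%. For 80% power a 2-df test needs a noncentrality of 9.64, so its efficiency is 6.23/9.64 = 0.646, a loss of about 35%.

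| Form of GRS in the product term | Information lost | Power (80% if continuous) |
|---|---|---|
| Continuous | 0% | 80% |
| Tertile trend, 1 df | about 21% | 70% |
| Tertile factor, 2 df | about 35% | 60% |

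**3. Cost of adding protein.** In a balanced two-by-two design the standard error of GRS × fat is 1/√(811 × 0.25) = 0.070 outcome SD per GRS SD. A simulated design gave 0.0703 for GRS × fat, both with fat terms alone and with the protein and GRS × protein terms added; GRS × protein itself also had 0.0703. A fat × protein term is orthogonal to both interactions under balance, so it should not change this. Each interaction uses all participants.

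**4. Detectable interaction at 80% power.** Continuous: 2.802 × 0.0702 = 0.197 outcome SD per GRS SD. Tertile trend: 0.197/√0.793 = 0.221. If only 80% of participants had a 2-year weight (an assumption), these become 0.220 and 0.247.

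**The case against.** The sentence about fat groups and tertiles describes changes by group. The primary question is carried by the product term that follows, which is introduced as addressing the diet interventions in general and could cover both factors or all four arms. The paragraph writes tertiles for the baseline comparison and for the group changes, but plain GRS in both interaction terms. That fits a continuous score in the tests, with tertiles for presentation, at least as well as the alternative.

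Much of this stands, and it rules out several stronger inferences:

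- A reader might infer that protein is never tested. The text supports only that no protein test is specified.
- A reader might infer that a fifth of the GRS information is discarded. That holds only if a tertile trend enters the test; the readings the text allows run from 0% to about 35%.
- A reader might take the "Standard Deviation" entry in section 5 to mean that the interaction will be reported as a mean and SD. That entry is a results-form field summarising the outcome and does not replace the interaction test.
- A reader might infer that GRS × fat is biased. Leaving protein out of a randomised, balanced design does not by itself do that.
- Nor can one say that the trial has no power to spare, because the documents give nothing from which to judge it.

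What the objection does not remove is the gap. Protein appears in no analysis sentence. The single product term is attached to models that name only fat groups, and one product with a two-level diet variable cannot carry both factors: that needs two terms, and four arms need 3 df. If a broader term was meant, the plan should say so.

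**Conclusion.** The concern holds as one of incomplete specification. The only diet contrast named is high versus low fat; no protein main effect or GRS × protein term is specified; and the GRS-diet term leaves both of its components undefined. The first two points follow directly from the text and need no assumption. The size of any power loss is conditional on how the GRS enters the product term, as tabulated above, and rests on a roughly normal score, a linear effect and two-sided testing. The correction is worth making because it closes the open choices in the primary test and uses the second randomised factor at almost no cost in precision.

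**What to change.** In the section 2 statistical paragraph:

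1. Specify one general linear model for 2-year weight change. Keep all the listed covariates, including the baseline value, and include fat, protein, fat × protein, continuous GRS (per SD), GRS × fat and GRS × protein.
2. Use the continuous GRS for every interaction p-value. Keep tertiles for tables and figures only.
3. State the order of testing: GRS × fat first, as the contrast the plan already names, then GRS × protein. In a fixed sequence, the second is confirmatory at 0.05 only if the first is significant; otherwise its estimate and interval are descriptive.
4. Report each interaction as a coefficient (kg per SD of GRS) with its 95% confidence interval.
5. Report GRS × fat × protein as exploratory. It should not serve as a gate for interpreting the two-way terms.

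The cost is a change of wording, a re-run and one extra interaction test. Because the plan makes no multiplicity adjustment, that test is not free in type I error; the stated order deals with this for the pair. The claim that GRS × fat loses essentially no precision assumes roughly equal allocation, which the documents do not state.

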**Arm/Group Description :**

diet 1: The study tests the effectiveness for weight loss and weight maintenance of four diets differing in macronutrient composition: moderate in fat (40% energy) with two different protein levels (15% and 25%), and low in fat (20% energy), also with 15% and 25% protein levels.

diet 2: The study tests the effectiveness for weight loss and weight maintenance of four diets differing in macronutrient composition: moderate in fat (40% energy) with two different protein levels (15% and 25%), and low in fat (20% energy), also with 15% and 25% protein levels.

diet 3: The study tests the effectiveness for weight loss and weight maintenance of four diets differing in macronutrient composition: moderate in fat (40% energy) with two different protein levels (15% and 25%), and low in fat (20% energy), also with 15% and 25% protein levels.

diet 4: The study tests the effectiveness for weight loss and weight maintenance of four diets differing in macronutrient composition: moderate in fat (40% energy) with two different protein levels (15% and 25%), and low in fat (20% energy), also with

15% and 25% protein levels.

**Period(s):** a 2-year randomized multicenter clinical trial .

**Period Title:** A 2-year randomized multicenter clinical trial

**Started:** September 2003

**Completed:** December 2010

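### The joint GRS-by-diet model adjusts for race only as a main effect, so a race-by-diet difference in weight change could appear as a gene-by-diet interaction

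*Combined protocol and SAP*

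**What the plan says.** Sections 2 and 5 make the gene-by-diet interaction on body weight change the primary outcome. The analysis is set out in the statistical paragraph of section 2:

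- **Covariates of the outcome models:** "Covariates adjustment included age, sex, race, physical activity, smoking, alcohol, seasonal variation, and the baseline value for the respective outcome in model". Race is in the list; site is not.
- **Interaction test:** "an interaction product term of GRS-diet was included in the models". No other product with diet is named.
- **Diet contrast:** the models "test changes in adiposity, glycemic and lipids traits in high-fat and low-fat diets groups according to tertiles of the GRS".
- **Score:** one score for all participants, with the SNPs "weighted by their effect sizes" from external meta-analyses. No standardisation within race and no genetic principal components are described.
- **Sites:** section 3 calls the study "a 2-year randomized multicenter clinical trial", and section 1 names two recruitment areas, Boston and Baton Rouge.

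The baseline comparisons across GRS tertiles are also made "with adjustment for age, sex, and race", so the plan itself treats race as related to the score or the outcomes. No race-stratified or single-race analysis is described, and the race distribution is not reported.

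**The concern.** Randomising diet protects the comparison between diets. It does not protect the comparison of diet effects across GRS levels, because participants are not randomised to a GRS. Allele frequencies, and so the score, can differ by ancestry. A race main effect removes race differences in mean weight change, but it assumes that the diet effect is the same in every race group. If that assumption fails and the score also differs by race, the GRS-by-diet term is the only place in the model where the race-by-diet difference can go.

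That coefficient is the primary result. It is tested at 0.05 with no multiplicity adjustment, so nothing else in the plan guards against a gene-by-diet finding that is really a race-by-diet finding.

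**Working it through.** The plan has no power or detectable-interaction figure to reproduce. The only figure at stake is the nominal 5% level.

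**Inputs from the documents:** N = 811; level 0.05 (sidedness not stated, two-sided used); race as a main effect; GRS-by-diet as the only diet product; high-fat versus low-fat contrast.

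**Assumed inputs, because the documents give none:** two race groups, with share m = 20% in the second; a GRS shift d between groups, in within-group SDs; a race-by-diet difference D in kg; outcome SD s of 7 or 8 kg; two equal diet groups; no true GRS-by-diet effect.

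**Formulas.** Let q = m(1 − m) and v = 1 + q·d².

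- Spurious interaction, per within-group SD of GRS: b = D·q·d / v
- Standard error of GRS-by-diet: SE = 2s / √(N·v)
- False-positive rate: Φ(−1.96 + b/SE) + Φ(−1.96 − b/SE)

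**One case in full** (d = 1, D = 4, s = 8): q = 0.2 × 0.8 = 0.16 and v = 1.16. Then b = 4 × 0.16 / 1.16 = 0.552 kg, SE = 16 / √(811 × 1.16) = 0.522 kg and b/SE = 1.058. The rate is Φ(−0.902) + Φ(−3.018) = 18.5%.

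The last column is a simulation of the model as written, with 2,000 trials per row.

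| d (SD) | D (kg) | s (kg) | b (kg) | SE (kg) | Rate, formula | Rate, simulated |
|---|---|---|---|---|---|---|
| 0.5 | 2 | 8 | 0.154 | 0.551 | 5.9% | 5.8% |
| 0.5 | 2 | 7 | 0.154 | 0.482 | 6.2% | 5.3% |
| 0.5 | 4 | 8 | 0.308 | 0.551 | 8.6% | 9.3% |
| 1.0 | 2 | 8 | 0.276 | 0.522 | 8.3% | 8.6% |
| 1.0 | 2 | 7 | 0.276 | 0.456 | 9.3% | 8.4% |
| 1.0 | 4 | 8 | 0.552 | 0.522 | 18.5% | 17.0% |
| 1.0 | 4 | 7 | 0.552 | 0.456 | 22.7% | 22.6% |
| 1.5 | 4 | 7 | 0.706 | 0.422 | 38.8% | 38.6% |

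**Other race mixes** (s = 8, d = 0.5 to 1.0, D = 2 to 4, simulated): 5.5% to 10.2% with a 10% share, and 7.8% to 30.5% with a 35% share.

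**Either condition absent** (d = 0 or D = 0, simulated): 4.5% to 5.3%.

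**With race-by-diet added:** 4.3% to 5.7% in every case at SD 8 kg, with mean bias within about 0.02 kg; 4.4% to 5.6% at SD 7 kg.

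**Site** (50:50 split, GRS shift of 0.5 SD between sites, SD 8 kg, 3,000 trials per case):

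- A 3 kg site main effect, left out of the model: 5.2%, no inflation.
- The same plus a 3 kg site-by-diet difference: 9.0% with site omitted, 9.6% with site as a main effect only, 5.6% with site and site-by-diet.

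**Cost in precision.** Once race-by-diet is in the model, only the within-race variation of the score is informative, so the standard error is multiplied by √v. At a 20% share:

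- d = 0.5: √1.04 = 1.02
- d = 1: √1.16 = 1.08
- d = 1.5: √1.36 = 1.17

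**The case against.** **The risk is doubly conditional.** It needs both a shift in this multi-SNP score between race groups and a diet effect on weight that differs by race. The documents show neither. At the mild end (0.5 SD, 2 kg) the inflation is hard to tell from none, and the 38% figure needs a 1.5 SD shift together with a 4 kg difference. This stands: the documents establish a possible bias, not an actual one.

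**Omitting site does no harm in itself.** A reader might infer that leaving site out of a two-area trial biases the interaction. Diet is randomised, so an omitted site main effect does not. Only a site-by-diet difference combined with a GRS difference between sites does, and then a plain site covariate does not help. This stands and shapes the remedy.

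**Separate models by diet group would avoid the problem.** If the tertile comparisons in the high-fat and low-fat groups are fitted separately, race is already estimated within each diet. This stands for those comparisons. It does not cover the joint product-term test, which addresses the primary question.

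**The remedy costs power.** It does, and most where the score and race overlap most. But that overlap is also what exposes the unadjusted test to bias, so the loss is no reason to prefer the smaller model.

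**Conclusion.** The point holds as a specification weakness in the joint GRS-by-diet test. Race as a main effect does not protect that test against a race-by-diet difference when the score also differs by race. Under the 20% share and the other stated assumptions, the false-positive rate runs from about 5% to 23% for shifts of 0.5 to 1.0 SD, with a spurious interaction of about 0.15 to 0.55 kg per SD of GRS. The documents supply no inputs from which to judge where in this range the trial lies, or whether it lies outside it.

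A further reading is tempting but unsupported. From "The Hardy-Weinberg equilibrium and comparison of categorical variables at baseline were assessed with chi-square test" a reader might infer that Hardy-Weinberg equilibrium was tested with all races pooled, and that sound SNPs would fail and leave the score. The text does not say whether the test is pooled or done within race, and it gives no rule for removing a SNP that fails. That reading forms no part of this conclusion.

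**What to change.** In the statistical paragraph of section 2:

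1. Add race-by-diet to the interaction model for the primary outcome, using the same diet contrast as the GRS-by-diet term.
2. Add site together with site-by-diet, on the same reasoning. Site as a main effect alone would not serve the purpose.
3. Report the GRS-by-diet estimate in the largest race group as a sensitivity analysis.

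Race is already in the model and the recruitment area of each participant should be on record, so no new data are needed. The cost is a few degrees of freedom and some precision. At a 20% share, race-by-diet raises the standard error of GRS-by-diet by about 2% at a 0.5 SD shift, 8% at 1 SD and 17% at 1.5 SD. By the same formula, site-by-diet with a 50:50 split and a 0.5 SD shift would by itself add about 3% (√(1 + 0.25 × 0.25) = 1.03). The single-race analysis uses fewer participants and will be less precise, so it should be read for consistency of the estimate and not for significance.

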**5. Outcome Measures**

**Outcome Measure Information:** Anthropometric measures were collected at baseline and 6, and 2 y according to standard protocols. BMI was calculated by dividing weight by the squared height of a participant. Dual-energy X-ray absorptiometry (DXA) scans were performed on a random subset of 50% of participants to assess body fat and BMD at baseline, 6 mo, and 2 y. Fasting blood samples were collected at baseline and 6 and 24 mo. Analyses for glucose and insulin were done from aliquoted serum at the Pennington Laboratory

with an immunoassay with chemiluminescent detection on an Immukite analyzer (Diagnostics Products Corp). Triglyceride, TC, LDL cholesterol, and HDL cholesterol were measured by using the Beckman Synchron CX7 analyzer (Beckman Coulter).

Genotyping has been described in detail previously. Briefly, DNA was extracted by using a QIAmp Blood Kit (Qiagen). Polymorphisms were genotyped by using the OpenArray SNP Genotyping System (BioTrove). The genotype success rate and replication concordance were >99%.

Outcomes included changes at 6 and 24 mo (determined as the difference from baseline) for anthropometric measures (weight, waist circumference, and BMI) and at 6 mo and 2 y for DXA body fat (total body fat, lean mass, and trunk fat) and BMD measures. The body-composition outcomes were selected to depict various adipose depots (ie, abdominal or central adiposity by using waist circumference and overall body fat by using BMI). The other endpoints for this study were changes in glycemic traits including fasting glucose, fasting insulin, insulin resistance and insulin sensitivity over the intervention. Homeostasis model assessment (HOMA) models were used to estimate insulin resistance (HOMA-IR), insulin sensitivity (HOMA-S), and  $\beta$ -cell function (HOMA-B), which were calculated by the following equations:

$$\begin{aligned}\text{HOMA-IR} &= (\text{fasting insulin } (\mu\text{U ml}^{-1}) \times \text{fasting glucose } (\text{mmol l}^{-1}))/22.5, \\ \text{HOMA-S} &= 22.5/(\text{fasting insulin } (\mu\text{U ml}^{-1}) \times \text{fasting glucose } (\text{mmol l}^{-1})) \text{ and} \\ \text{HOMA-B} &= (20 \times \text{fasting insulin } (\mu\text{U ml}^{-1})) / (\text{fasting glucose } (\text{mmol l}^{-1}) - 3.5).\end{aligned}$$

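### Tertile contrasts of the genetic risk score on fasting glucose change are adjusted for baseline glucose, which the score itself is built to raise, so they can show an effect on change when there is none

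*Combined protocol and SAP*

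**What the plan says.** All the planned tests are described in section 2 (Design and Methods).

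- **Score.** Each SNP's weight is its "coefficient of each SNP for higher levels of fasting glucose".
- **Aim.** The investigators set out to "examine whether the genetic variation affected glycemic, waist circumference, body weight, visceral fat, lipids, and bone mineral density (BMD) changes" under the dietary intervention.
- **Tertile test.** General linear models test changes in the traits "in high-fat and low-fat diets groups according to tertiles of the GRS". The covariates are age, sex, race, physical activity, smoking, alcohol, season "and the baseline value for the respective outcome in model".
- **Interaction test.** A GRS-by-diet product term is added to these models.
- **Secondary test.** Linear mixed models include a GRS-by-time term. Whether baseline is a covariate there is not stated.
- **Baseline comparison.** Continuous variables "according to tertiles of the GRS(genetic risk score) at baseline were tested using general linear models", so baseline differences by GRS are foreseen.

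Section 5 (Outcome Measures) lists "changes in glycemic traits including fasting glucose, fasting insulin, insulin resistance and insulin sensitivity over the intervention" as endpoints, with fasting blood at baseline, 6 and 24 months. Section 4 (Baseline Characteristics) states what is randomised: "Participants were randomly distributed to one of four diets". All tests use P < 0.05 without multiplicity adjustment. The plan describes no GRS contrast on change that leaves out the baseline covariate.

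**The concern.** Baseline adjustment suits a randomised contrast, because the arms have the same expected baseline. GRS tertiles are inherited, and by the construction of the score the upper tertile should start with higher fasting glucose. The genotype goes on acting after baseline, so each tertile regresses towards its own mean and not towards a common one. Holding baseline glucose equal compares a high-GRS person who is low for that group with a low-GRS person who is high for that group. At follow-up the first tends to drift up and the second down, even if neither group's mean change differs.

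The error has a predictable direction: participants with a high score appear to have a less favourable glucose change on either diet. The risk is a published statement that the score predicts poorer glucose response, resting only on the choice of covariate.

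**Working it through.** The documents contain no power or effect-size calculation, so there is no figure of the plan's own to reproduce.

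**Algebra.** Let the GRS groups differ by d at baseline and by d at follow-up, so the true difference in change is d − d = 0. Let b be the slope of follow-up on baseline within GRS groups. The baseline-adjusted difference in change is (difference at follow-up) − b × (difference at baseline) = d − b·d = d(1 − b). This is zero only if d = 0 or b = 1.

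**Inputs from the documents.** There are 811 participants and tests are at 0.05 (two-sided assumed). With equal allocation, also assumed, there are about 405 per fat level and 405/3 = 135 per tertile.

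**Inputs assumed, not in the documents.** The GRS explains R² = 1%, 2% or 4% of baseline glucose variance. The baseline to follow-up correlation r is 0.5 to 0.8 with equal variances, so b = r. There is no dropout.

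**One cell by hand (R² = 2%, r = 0.7).**
- The baseline shift per SD of GRS is √0.02 = 0.141 SD of glucose.
- The spurious coefficient is 0.141 × (1 − 0.7) = 0.042 SD per SD of GRS.
- The top and bottom thirds of a normal score lie 2.18 SD apart, so the spurious tertile difference is 2.18 × 0.0424 = 0.092 SD.
- The residual SD is √(0.98 × (1 − 0.49)) = 0.707, and the standard error is 0.707 × √(2/135) = 0.086.
- The ratio is 0.0925/0.086 = 1.08, which gives a rejection probability of about 0.19. Simulation gave 0.179. It is slightly lower because the baseline covariate absorbs some of the GRS spread within tertiles.

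**Simulation, top versus bottom tertile in one fat group, no true effect on change (3,000 runs per cell).**

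| R² | r = 0.5 | r = 0.7 | r = 0.8 |
|---|---|---|---|
| 1% | 0.176 | 0.114 | 0.092 |
| 2% | 0.303 | 0.179 | 0.137 |
| 4% | 0.530 | 0.311 | 0.228 |

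With the baseline covariate removed, the same cells gave 0.045–0.056. At R² = 0 the adjusted test rejected at 0.053–0.058, so the excess comes from the link between GRS and baseline.

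**Overall tertile test (2 degrees of freedom), one fat group.** Separate simulations over the same range gave about 8–44% with baseline adjustment and about 4–7% without it. The middle case (2%, r = 0.65) gave 17%. The spurious top-versus-bottom difference runs from 2.18 × 0.1 × 0.2 = 0.04 SD to 2.18 × 0.2 × 0.5 = 0.22 SD.

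**Tests that are not affected.**
- *GRS-diet product term.* Diet is randomised, so d(1 − b) is the same on each diet and cancels. In the baseline-adjusted models the mean coefficient was about 0 and rejection was 0.044–0.061.
- *GRS-by-time between 6 and 24 months.* A baseline covariate is constant within a person, so if it enters with one coefficient for both visits it cancels from this contrast. Simulated rejection was 4.7–5.6%.

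**Cost of removing the covariate.** The standard error changes by √(2(1 − r)/(1 − r²)) = √(2/(1 + r)). This is 1.05 at r = 0.8 and 1.15 at r = 0.5.

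**The case against.** The strongest reply is that every stated outcome, primary and secondary, is a gene-diet interaction, and that term is unbiased. This stands. A reader might infer that the trial's main question is compromised, but the documents do not support that. What remains exposed is a GRS contrast within each fat group. It is not a named outcome, although section 2 specifies a test of it and states an aim that it would be used to answer. That aim does refer to change in response to the diets, yet the tertile contrasts within fat groups would still be read as GRS effects.

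A second reply is that baseline adjustment validly answers another question: whether the GRS predicts change among people with equal baseline glucose. That is also true. But the plan does not say this is the question meant, its aim speaks simply of changes, and no unconditioned contrast is offered.

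Three further inferences go beyond the documents.
- *The mixed model shares the bias.* The test named there is GRS-by-time, which a baseline covariate entered once does not bias.
- *Insulin and HOMA are equally affected.* The weights are for glucose. HOMA contains glucose, so some carry-over is plausible, but the bias exists only as far as the GRS shifts each trait's own baseline. For body weight, nothing in the documents ties the glucose-weighted score to baseline weight.
- *Glucose at a visit rests on a single sample.* Section 5 does not give the number. The argument needs only b < 1.

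Finally, R² and r are assumptions. Excluding people with drug-treated diabetes could weaken the link between GRS and glucose in this sample. At the mildest values used, the excess over 5% is small.

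**Conclusion.** The point holds for GRS-tertile contrasts on fasting glucose change within the fat groups. The existence of the bias needs only a baseline glucose difference by GRS, which the score is built to produce, and a slope below 1. Its size depends on the assumed values: about 8–44% false positives per fat group for R² of 1–4% and r of 0.5–0.8 with complete data, against about 4–7% without the baseline covariate. The primary and secondary interaction tests stand as planned. This is a worthwhile correction to a supporting analysis and no reason to doubt the main one.

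**What to change.** In the statistical analysis paragraph of section 2:

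1. Keep the baseline value as a covariate in the GRS-diet test and in any diet comparison.
2. For GRS-tertile contrasts on fasting glucose change, and on any glycemic trait whose baseline differs by GRS, fit a longitudinal model with baseline, 6 and 24 months all as responses. Read the effect on change from the GRS-by-visit contrasts against baseline. Change without the baseline covariate is an acceptable substitute only if the data are complete; with missing visits the two are not equivalent.
3. Report the baseline-adjusted contrast beside it, labelled as the effect among people with equal baseline.
4. Claim a GRS effect on glucose change only if the unconditioned contrast supports it.
5. State whether baseline is a covariate or a response in the mixed model.

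This costs a few sentences of SAP text and one further model on existing data. The standard error of the GRS contrast becomes about 5–15% larger.
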